## 10.2. Potential Benefits

The main benefit of this study is that patients may experience improved glucose control. Otherwise subjects should not expect to benefit from participation in this study; however, they may gain increased awareness of emerging technologies for diabetes management as a result of their participation.

## 10.3. Risk-Benefit Rationale

The main benefit of this study is that patients may experience improved glucose control. The risk, as with all automated systems, is the possibility of an increase in hypoglycemia. To address this risk, many scenarios have been modeled and the risk is effectively minimized by a variety of safety checks that are an integral part of the revised device algorithm.

# 11. Adverse Events Assessments

## 11.1. Adverse Events

Throughout the course of the study, investigational centers will make all efforts to remain alert to possible reportable adverse events (AEs) or untoward findings. The study personnel will elicit reports of AEs from the subject at each visit (including phone calls) documenting the medical diagnosis, date of event start and end, causality (relationship to device or procedure), treatment, outcome, and description that includes the details of the event.

## 11.2. Definitions and Classification of Adverse Events

Medtronic uses the definitions provided in NMPA (former CFDA) Order No. 25, ISO 14155:2011 and 21 CFR 812 for AE definitions. ISO14155:2011 definitions are used for AE classifications while expedited reporting to local authorities/EC should be done based on local definitions of local regulations. Where the definition indicates "device", it refers to any device used in the study. This might be the device under investigation, or any market released component of the system. Medtronic follows MEDDEV 2.7/3 revision 3 guidelines for classifying causality levels; but will apply these causality definitions across all events, not only serious adverse events and definitions have been adapted accordingly.

**Severe Hypoglycemia** is an event requiring assistance of another person due to altered consciousness to actively administer carbohydrate, glucagon, or other resuscitative actions. This means that the subject was impaired cognitively to the point that he/she was unable to treat his or her self, was unable to verbalize his or her needs, and was incoherent, disoriented and/or combative.

These episodes may be associated with sufficient neuroglycopenia to induce seizure or coma. Plasma glucose measurements may not be available during such an event, but neurological recovery attributable to the restoration of plasma glucose to normal is considered sufficient evidence that the event was induced by a low plasma glucose concentration. (**Adapted from American Diabetes Association Workgroup on Hypoglycemia, Diabetes Care 28:1245-1249, 2005**)

**Severe Hyperglycemia** is defined as hyperglycemia (blood glucose greater than ( $>$ ) 300 mg/dL [16.7 mol/L]) with blood glucose ketones greater than ( $>$ ) 1.5 mmol/L, urine ketones moderate or large, or accompanied by symptoms of nausea, vomiting or abdominal pain.

**Diabetic Ketoacidosis/DKA** diagnostic criteria: blood glucose greater than ( $>$ ) 250 mg/dL or greater than ( $>$ ) 13.9 mmol/L, arterial pH less than ( $<$ ) 7.3, bicarbonate less than ( $<$ ) 15mEq/L, moderate ketonuria or ketonemia and requiring treatment within a health care facility. (**American Diabetes Association-Diabetes Care, Volume 27, Supplement 1, January 2004; S94-S102**)

Hyperglycemic events will be recorded as DKA if the event includes the presence of all of the following:

- Arterial blood pH less than ( $<$ ) 7.30 or serum bicarbonate less than ( $<$ ) 15mEq/L
- Blood glucose greater than ( $>$ ) 250 mg/dL (or greater than ( $>$ ) 13.9 mmol/L)
- Serum ketones or large/moderate urine ketones
- Symptoms such as polyuria, polydipsia, nausea, or vomiting
- Treatment provided in a health care facility

## Adverse Event (AE) (ISO 14155-2011)

Any untoward medical occurrence, unintended disease or injury, or untoward clinical signs (including abnormal laboratory findings) in subjects, users or other persons, whether or not related to the investigational medical device.

**Note 1:** This definition includes events related to the investigational medical device or the comparator.

**Note 2:** This definition includes events related to the procedures involved.

**Note 3:** For users or other persons, this definition is restricted to events related to investigational medical devices.

## Adverse Event (AE) (NMPA (former CFDA) Order No.25 Article 93)

The medical events with disadvantages occurred during the clinical trials, no matter whether they are related to investigational medical devices or not.

## Adverse Device Effect (ADE) (ISO 14155-2011)

Adverse event related to the use of an investigational medical device.

**Note 1:** This definition includes adverse events resulting from insufficient or inadequate instructions for use, deployment, implantation, installation, or operation, or any malfunction of the investigational medical device.

**Note 2:** This definition includes any event resulting from use error or from intentional misuse of the investigational medical device.

## Serious Adverse Event (SAE) (ISO 14155-2011)

Adverse event that

- Led to a death
- Led to a serious deterioration in the health of the subject, that either resulted in
  1. a life-threatening illness or injury, or
  2. a permanent impairment of a body structure or a body function, or
  3. in-patient\* or prolonged hospitalization, or
  4. medical or surgical intervention to prevent life-threatening illness or injury or permanent impairment to a body structure or a body function
- Led to foetal distress, foetal death or a congenital abnormality or birth defect

**Note:** Planned hospitalization for a pre-existing condition, or a procedure required by the CIP, without a serious deterioration in health, is not considered a serious adverse event.

*\*For the purpose of this study, Inpatient Hospitalization is defined as: admission to the hospital for a period of 24 hours or more based on urgent medical need rather than elective admission*

For the purpose of this study, the term "life-threatening" in the definition of "serious" refers to an event in which the patient was at risk of death at the time of the event; it does not refer to an event which hypothetically might have caused death if it were more severe. (ICH Topic E 2 A Clinical Safety Data Management: Definitions & Standards for Expedited Reporting. EMEA 2006)

## Serious Adverse Device Effect (SADE) (ISO 14155-2011)

Adverse device effect that has resulted in any of the consequences characteristic of a serious adverse event

## Serious Adverse Event (SAE) (NMPA (former CFDA) Order No.25 Article 93)

Any untoward medical occurrence during the clinical trial: results in death or serious deterioration in health; life-threatening diseases or injuries; causing permanent damage to the body structure or function; requires hospitalization or prolongation of hospitalization; requires medical operations or intervention for preventing from persistent or significant disability/incapacity; results in fetal distress, fetal death, or congenital anomaly/birth defect.

## Unanticipated Adverse Device Effect (UADE) (21 CFR 812.3(s))

Any serious adverse effect on health or safety or any life-threatening problem or death caused by, or associated with, a device, if that effect, problem, or death was not previously identified in nature, severity, or degree of incidence in the investigational plan or application (including a supplementary plan or application), or any other unanticipated serious problem associated with a device that relates to the rights, safety, or welfare of subjects.

---

*Medtronic Confidential*

## 11.3. Reporting of Adverse Events

The investigator or designee will record ALL AEs while the subject is enrolled in the clinical study. Each AE needs to be assessed for its device or procedure relatedness. A device related AE is associated with the use of the study device (e.g. infection of sensor site or infusion set occlusion resulting in DKA). A procedure related AE is associated with testing related to the study procedures specified in the CIP (e.g. IV insertion pain).

Examples of device or procedure related AEs include:

- **Device** related (ADE): insertion site infection
- Serious adverse **device effect**: cellulitis at device insertion site requiring hospitalization
- **Procedure** related AE: bruising at IV insertion site

Subjects participating in the study have diabetes and are expected to experience hypoglycemia and or hyperglycemia. These normal events are not expected to be reported to sponsor on an AE eCRF as this is not considered an untoward event, but rather an expected occurrence. Any glycemic excursion that meets the protocol definition of Severe Hypoglycemia, Severe Hyperglycemia or DKA is considered an untoward event and a worsening from the subject's baseline and would be reported to sponsor on an AE eCRF.

Baseline medical conditions should only be reported to sponsor on an AE eCRF if there is a worsening from the subject's baseline. For example, a subject previously diagnosed with Asthma is hospitalized for severe asthma attack would be a reportable event.

Adverse events will be documented in the subject source file and reported to sponsor on an eCRF. The investigational center is responsible for documentation of AEs including obtaining source documents related to the event, such as emergency medical technician/paramedic reports, hospital records (admission summary; lab results, test results, discharge summary) or device uploads to support the event. Source documents will be reviewed to determine if additional AEs have occurred and require reporting.

Narratives gathered from completed questionnaires will not provide the basis of an AE report however could lead to discussions that result in the identification of a reportable AE.

Adverse events that have not resolved at the time of the subject's discontinuation or completion of the study should have an "outcome" of Not Recovered/Not Resolved at study end in subject source and on an eCRF. The investigator should ensure that subject is aware of any follow-up or additional treatment that is required for any ongoing AE at end of study participation; however, there will be no eCRF entry for the ongoing follow-up.

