# CIP329 Clinical Investigation Plan

10939060DOC

Version C

Page 54 of 99

Medtronic

	Run-in Period				Study Period				
	Visit 1 (O)	Visit 2 (O)	Visit 3 (O)	Visit 4 (O)	Visit 5,6 and 7 (O/T)	Visit 8 and 9 (O/T)	Visit 10 (O)	Visit 11 (O)	Visit 12 (O)
O= Office T= Telephone									
medical condition, such as sickness or glycemic problems.									

 
Instruct subject to call the investigational center to report any changes to their health status (see adverse event definition).
 
Ask subjects about number of days missed at work or school, record on applicable CRF
 
									
Ask subjects about device performance issues and if they called the 24 -Hour Technical Support (TS) to report them		x	x	x	x	x	x	x	x

 
Instruct/Remind subjects to contact the Medtronic 24-Hour TS in the event they experience problems with their study devices.
 
									
Pump Training - General									
Instruct subjects on the use of the study pump; provide Pump User Guide, Getting Started Guide, etc.		x							
Instruct/remind subjects that they must upload the MiniMed 670G pump to CareLink™.		x	x	x	x	x	x	x	x

 
Uploading may occur daily/weekly based on sponsor instruction
 
									
Verify that the pump is set Manual Mode (Sensor Augmented Pump only) SmartGuard™ features should not be activated		x							
Instruct subjects that the low glucose alert limit (low glucose threshold alert based on sensor glucose reading) is recommended to be set at 70 mg/dL (3.9 mmol/L)		x (as applicable)	x	x					
Instruct subjects that the high glucose alert limit (high glucose threshold alert based on sensor glucose reading) is recommended to be set at 300 mg/dL (16.7 mmol/L)		x (as applicable)	x	x					
Pump Training - Auto Mode Instructions									

*Medtronic Confidential*

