
 
• Hypoglycemia
 
• Severe hypoglycemia
 
• Hyperglycemia
 
• Diabetic ketoacidosis User Entry Error             
 
◦ Patient administering boluses by entering false carb doses leading to hypoglycemia or hyperglycemia
 
◦ Patient entering false glucose values for any reason leading to hypoglycemia and hyperglycemia
 
◦ Patient entering false BG values for calibration leading to hypoglycemia or hyperglycemia
 
 
 
• Sensor failure resulting from patient failure to calibrate leading to hypoglycemia or hyperglycemia
 
• Sensor over-reading resulting in hypoglycemia
 
• Sensor under-reading resulting in hyperglycemia
 
• Sensor missed transmission, or any other fault resulting in no SG value, leading to hyperglycemia or hypoglycemia
 
• Voluntary insulin delivery (with the pump or with a syringe) immediately prior to entering Auto Mode may result in severe hypoglycemia despite shutting down insulin delivery by the algorithm
 
• Hypoglycemia related to patient taking insulin via injection while in Closed Loop (Auto Mode)
 
• Hypoglycemia or hyperglycemia related to entering or exiting Closed Loop (Auto Mode)
 
• Insulin over-delivery due to potential interference from acetaminophen
 
• Cyber security hacking into pump
 
	
 
• Follow the provided user guides for insulin pump management.
 
• Training prior to study on device use and diabetes management principles and told to call with problems.
 
• Check SMBG 4-6 times a day.
 
• Instructed to have glucose on hand for hypoglycemia
 
• Subjects will be instructed to consider avoiding the use of products containing acetaminophen
 
• If acetaminophen is taken, subjects will be instructed to use additional BG meter readings (they are not to calibrate with those readings) to verify their glucose levels.
 
• If acetaminophen is taken, subjects should consider exiting Auto Mode
 
• Pump has cybersecurity encryptions to prevent hacking.
 

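### Section 11.3 exempts glycemic excursions below three severity definitions from AE recording, with no exception for serious ones or those due to device malfunction or use error, in conflict with the ADE and SAE definitions and Table 3

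*Protocol*

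**What the plan says.** Protocol Section 11.3 notes that subjects with diabetes are expected to have hypo- and hyperglycemia, and then says: "These normal events are not expected to be reported to sponsor on an AE eCRF as this is not considered an untoward event". The next sentence restores part of what was removed: "Any glycemic excursion that meets the protocol definition of Severe Hypoglycemia, Severe Hyperglycemia or DKA is considered an untoward event". It names those three categories and no others.

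Section 11.2 sets the three thresholds.
- Severe hypoglycemia "is an event requiring assistance of another person due to altered consciousness to actively administer carbohydrate, glucagon, or other resuscitative actions".
- Severe hyperglycemia needs blood glucose above 300 mg/dL together with raised blood ketones, "urine ketones moderate or large, or accompanied by symptoms of nausea, vomiting or abdominal pain".
- DKA is recorded only if every item on a list is present: pH below 7.30 or bicarbonate below 15 mEq/L, glucose above 250 mg/dL, ketones, symptoms, and treatment in a health care facility.

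Section 11.2 also defines an ADE as an adverse event related to use of the device. Its notes take in use error, inadequate instructions "or any malfunction of the investigational medical device". The ISO definition of an SAE is an adverse event with one of several outcomes. One branch begins "Led to a serious deterioration in the health of the subject, that either resulted in" and lists in-patient hospitalization, which this study takes as an urgent admission of 24 hours or more. The NMPA definition likewise starts from an untoward occurrence.

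Table 3 (Section 9.2) tells staff at each visit to record as an AE any health change that is a new condition or a deterioration of an existing "medical condition, such as sickness or glycemic problems". It states no severity threshold.

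**The concern.** Excursions caused by the sensor, algorithm, pump or user are a main way in which a hybrid closed loop system can harm. Section 10.3 names more hypoglycemia as the risk of an automated system. Section 10.1 lists, under closed loop therapy, "Sensor over-reading resulting in hypoglycemia" with no severity limit, and lists severe hypoglycemia as a separate item. Section 11.3 nevertheless decides by severity alone whether an excursion counts as an adverse event.

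Safety is part of the primary objective, and the study is meant to support registration. If sub-threshold excursions due to a device fault are left out of AE recording, the device-related AE count is biased downward. If the SAE status of a hospitalized excursion is unclear, so are two steps that depend on it: the 24-hour report to the local authority in Table 4 and review by the Clinical Events Committee (Section 12.1). Centers that give more weight to Table 3 could also count differently from those that give more weight to Section 11.3.

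**Working it through.** No arithmetic decides this point. The check applies the definitions to hypothetical cases.

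1. **Chain of definitions.** An AE is an untoward occurrence, an ADE is an AE related to the device, and an SAE is an AE or untoward occurrence with a serious outcome. Whatever Section 11.3 declares not untoward drops out at the first link and is never assessed for causality or seriousness.

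2. **Cases.**

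| Case | Meets one of the three definitions? | Under 11.3 read literally | Under other text |
|---|---|---|---|
| A. Sensor over-reads in Auto Mode; meter shows 45 mg/dL; subject is alert and self-treats | No: no assistance, no altered consciousness | Not an AE, so not an ADE | ADE by the notes in 11.2; listed risk in 10.1 |
| B. Occluded infusion set; glucose 350 mg/dL, no ketones, no symptoms | No: above 300, but no ketones or symptoms | Not an AE; device deficiency form only, if reported | ADE by the notes in 11.2 |
| C. Glucose 280 mg/dL, ketones, vomiting, pH 7.32, bicarbonate 17 mEq/L; urgent admission of more than 24 h | No: 280 is not above 300; 7.32 is not below 7.30 and 17 is not below 15 | Not an AE, so not an SAE | SAE by both definitions in 11.2; deterioration under Table 3 |
| D. Occluded infusion set leading to DKA | Yes | AE, assessed for causality | Same; 11.3 uses it as an example |

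3. **Cases A and B.** The rule gives a result that the ADE definition does not intend: an event due to malfunction or use error is kept out of ADE assessment only because it was not severe.

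4. **Case C.** The passages disagree. Section 11.3 says that an excursion meeting one of the three definitions is a worsening from baseline, and names no other excursion that is. The SAE definitions, the separate SAE notification in Section 11.4 and Table 3 point towards recording it.

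5. **Does other capture close the gap?** Section 13 requires an eCRF for each reported device deficiency, and deficiencies include malfunctions and use errors. That form records the fault. Staff must still decide whether an AE occurred, which takes them back to Section 11.3. The sensor glucose endpoints give percentages of time with no cause or outcome, and a sensor that over-reads can hide the low in its own trace. SAP Sections 7.9.3 and 7.10 repeat the AE categories and add no rule.

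**The case against.** The best defence is that a severity cut-off with separate device deficiency capture is a coherent way to keep thousands of routine readings off AE forms. Much of that defence stands.

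- A reader might infer that device-caused excursions are never recorded. The documents do not support this. DKA from an occluded infusion set is an example of a device-related AE in Section 11.3, and the worked example in Section 11.6 rates severe hyperglycemia with a bent cannula as causal. Only sub-threshold excursions are at issue.
- A reader might also infer that hospitalized sub-threshold excursions are certain to be lost. That cannot be shown. The exemption speaks of normal events and does not mention ketosis or vomiting. Section 11.3 makes worsening of a baseline condition reportable, with a hospital admission as its example, and has hospital records reviewed for further AEs. Section 11.4 lists SAEs in addition to the three glycemic categories. The result is a conflict between passages, not a certain omission.
- Table 3 can be read together with Section 11.3, since both turn on deterioration. That centers will in fact count differently is a plausible risk and not a demonstrated one.
- Reported faults are not lost. They reach the deficiency eCRF and are summarized, and meter values are uploaded (Section 16.3.1.3).

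The defence does not supply an AE record and a causality rating for cases such as A and B, or a clear rule for case C.

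**Conclusion.** Wrong as written: the AE reporting rule in Section 11.3 conflicts with the ADE and SAE definitions in Section 11.2, with SAE notification in Section 11.4 and with the Table 3 prompt. What is lost is AE and ADE recording, with causality assessment, of sub-threshold excursions caused by a device fault or use error. What is ambiguous is the SAE status of a hospitalized sub-threshold excursion.

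The conclusion assumes that sites apply Section 11.3 as worded. The direction is towards a lower device-related AE count. The primary time-in-range test is unaffected, and no AE rate is tested.

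The size cannot be estimated from the documents. A reader might try to scale from the cited US trial: 28 / 12,389 = 0.00226 device-related AEs per patient-day. Over 50 x 30 = 1,500 Auto Mode days this gives about 3.4 events, and over 75 x 30 = 2,250 days about 5.1. That shows the expected count is small. It does not show what share would be missing, because the documents give no rate for sub-threshold device-caused excursions and do not say whether the 28 events included any.

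**What to change.** In Section 11.3, at the end of the sentence that calls these excursions expected, add: *except that any hypo- or hyperglycemia that (i) meets a seriousness criterion in 11.2, or (ii) is associated with a recorded device deficiency or use error, is recorded on the AE eCRF and assessed for causality.* Cross-refer the adverse-event row of Table 3 to this sentence.

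Do not use a trigger based on possible relatedness. Section 11.6 puts cases that cannot be assessed into the category Possible, so such a trigger would bring in many ordinary excursions. The two triggers above rest on facts that sites already document.

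The cost is a short protocol amendment, a few more AE eCRFs and possibly a slightly less favourable device-related AE count. Ordinary excursions stay exempt. An excursion whose device cause is never noticed or reported would still be missed unless it is serious or meets one of the three definitions. The change concerns recording only and leaves the care of subjects as it is.

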## 9.10. Subject Withdrawal or Discontinuation

Subjects may choose to withdraw from the study at any time by notifying investigational center staff of their intent.

If a subject chooses to end his or her study participation or if the subject is removed from the study at the investigator's discretion or for failure to meet the study requirements, the reason for withdrawal must be documented. All study devices and supplies must be returned (as applicable) and documented both in source documents and on an eCRF.

Subjects may also be withdrawn from the study at the discretion of the investigator. A subject may be withdrawn from the study if:

- In the opinion of the investigator, the subject's health or safety would be compromised by continuing in the study
- In the opinion of the investigator, it is in the subject's best interest to discontinue participation in the study
- The subject is found to no longer meet all inclusion criteria, or is found to meet one or more exclusion criteria
- The subject fails to comply with one or more study requirements
- The subject is lost to follow up
- During the course of the study, subject begins participation in another investigational study (drug or device).
- During the course of the study, subject begins abusing illicit drugs.
- During the course of the study, subject begins abusing alcohol.

- During the course of the study, subject begins using pramlintide (Symlin), DPP-4 inhibitors, liraglutide (Victoza or other GLP-1 agonists), metformin, canagliflozin (Invokana or other SGLT2 inhibitors).
- During the course of the study, subject receives red blood cell transfusion or erythropoietin.
- During the course of the study, the subject demonstrates that he/she is not able to comprehend instructions for study procedures, as evaluated by the appropriate research staff.
- During the course of the study, subject is taking oral, injectable, or IV glucocorticoids
- During the study, (female) subject becomes pregnant.
- During the study, the subject experiences one severe hypoglycemic episode
- During the study, the subject experiences one episode of DKA
- During the study, subject has a cardiovascular event or any vascular event such as stroke.

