## Lost to Follow-up

In the case that the subject is determined to be lost to follow-up, details of a minimum of two attempts and the method of attempt (e.g., one letter and one phone record or two letters) to contact the subject must be recorded. In addition, the requirements set by the governing EC for subjects lost to follow-up must be followed.

Documentation of the reason(s) leading to subject withdrawal will be kept in the subject's source documentation.

Upon exiting from the study, no further study data will be collected or study visits will occur for the subject. All data available through the time of the subject's exit will be used for analysis. In the event of study exit, the investigator should discuss with the subject the plans for future care and treatment. The investigator should explain that the subject will continue to receive standard medical care. Alternative treatment, such as medication options or follow-up through standard of care procedures instead of study procedures, and medical consequences should also be discussed. Source documentation of this conversation recommended. The investigator must notify the subject of any significant new findings that may become available during the course of the study, which are pertinent to the safety and well-being of the subject.

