## 9.11. Stopping Rules

### 9.11.1. Subject Stopping Rules

Any event of DKA or severe hypoglycemia will result in withdrawal of subject from study.

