## 11.4. Notification of Adverse Events

### Sponsor Notification:

The investigational center staff must report all AEs to Medtronic in a timely manner. All Severe Hypoglycemia, Severe Hyperglycemia, DKA, SAE, and SADE should be reported as soon as possible (desired within 24 hours of investigator or study coordinator awareness) to Medtronic. Refer to Table

4 below for Investigator Reporting Requirements. For the previously mentioned events, the AE eCRF will be completed with all known details as soon as possible, this will serve as notification to Medtronic. If the study database cannot be accessed due to technical problems, contact the sponsor via email at [[contact]](mailto:[contact]) and provide the known details of the event. Once the access issue has been corrected, the event should be entered onto an AE eCRF.

Source documents that support the event (e.g. clinic notes, hospital admission and discharge records, lab reports, EMT reports, ER/Urgent Care) should be provided to the sponsor via the Medtronic BOX safety folder. All source documents/medical records should be redacted. Each source page should be identified with the subject ID.

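### Serious adverse events, DKA and severe hypoglycemia still open at study exit have no route for their final outcome to enter the study data

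*Protocol*

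**What the plan says.** Section 11.1 asks sites to elicit adverse events at each contact, "documenting the medical diagnosis, date of event start and end, causality (relationship to device or procedure), treatment, outcome".

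Section 11.3 covers events unresolved when the subject discontinues or completes. The outcome is to be "Not Recovered/Not Resolved at study end in subject source and on an eCRF". The investigator makes sure the subject knows what further care is needed; "however, there will be no eCRF entry for the ongoing follow-up".

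Section 9.10, under Lost to Follow-up, states: "Upon exiting from the study, no further study data will be collected or study visits will occur for the subject".

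Section 9.11.1, with the same wording in the Synopsis, states: "Any event of DKA or severe hypoglycemia will result in withdrawal of subject from study". The list in section 9.10 is permissive. It opens with "A subject may be withdrawn from the study if" and includes "During the study, the subject experiences one episode of DKA", with a matching entry for one severe hypoglycemic episode.

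Section 11.4 (Sponsor Notification) asks for supporting material to go to the sponsor: "Source documents that support the event (e.g. clinic notes, hospital admission and discharge records, lab reports". SAP sections 7.9.3 and 7.10 collect adverse events from consent to study end and say nothing about follow-up to resolution.

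**The concern.** Two rules combine. One stops data collection when a subject exits; the other makes two of the named safety events a cause of exit. For an event still running at that moment, the eCRF carries a fixed not-recovered code, whatever happens afterwards. The same holds for an SAE that starts shortly before Visit 12.

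Safety is part of the primary objective, and the results go to the regulator for registration. Severe hypoglycemia and DKA are named safety measures. Device-related cases, together with UADEs, go to the Clinical Events Committee (CEC), which advises whether the study continues. What is at stake is the last part of the record for a very small number of events: when the event ended, whether the subject recovered, and whether there were sequelae or a death.

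**Working it through.** The check is mainly a reading of the provisions together, followed by a calculation of scale. The plan gives no figure of its own on this point to reproduce.

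**Step 1: what closes the record.** Section 11.3 applies at discontinuation or completion. It fixes the code and excludes an eCRF entry for continuing follow-up. The sentence in section 9.10 sits under the Lost to Follow-up heading, but it is worded for any exit. Section 11.3 reaches the same result for adverse events without it.

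**Step 2: is any event exempt?** No exemption for SAEs, SADEs, UADEs, DKA or severe hypoglycemia appears in protocol sections 9.10, 9.11, 11.1 to 11.5 or 12.1, or in SAP sections 7.9.3 and 7.10. The termination visit in section 16.11.2 applies when a center is suspended or terminated, not when one subject is withdrawn.

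**Step 3: does the event itself cause exit?** Section 9.11.1 and the Synopsis say that it will. Section 9.10 says that it may. The Auto Mode instructions in Table 3 recommend turning Auto Mode off or changing to injections after either event and do not mention withdrawal. These places must be reconciled. Under either wording, a subject who is withdrawn meets the cut-off in Step 1. No section says when withdrawal takes effect relative to resolution of the event.

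**Step 4: what is lost and what is kept.**

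| Item | Status for an event open at exit |
|---|---|
| Occurrence (incidence) | Kept: the event precedes the exit |
| Diagnosis, start date, causality, treatment to date | Kept under section 11.1 |
| End date | Not recorded if after exit |
| Final outcome, sequelae, later death | Not on the eCRF; may appear in source if discharge records are obtained |

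**Step 5: scale.** Inputs:
- No severe hypoglycemia or ketoacidosis in 12,389 patient-days of the pivotal trial (protocol section 4.1.2).
- Up to 75 subjects, a run-in of up to 35 days and a study period of up to 33 days (section 6).

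With zero events, the one-sided 95% Poisson upper bound on the rate is −ln(0.05) / 12,389 = 2.996 / 12,389 = 0.000242 per patient-day.

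- Whole participation: 75 × (35 + 33) = 5,100 patient-days; 5,100 × 2.996 / 12,389 = 1.23 expected events.
- Study period only: 75 × 33 = 2,475 patient-days; 2,475 × 2.996 / 12,389 = 0.60 expected events.

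These are upper bounds on the number of DKA and severe hypoglycemia events of any duration. The number still open at exit cannot be larger and is probably smaller. The documents give no rate for other SAEs, so the number open at Visit 12 cannot be estimated from them.

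**The case against.** The strongest reply is that the plan sets a deliberate, explicit cut-off and that little depends on what lies beyond it. Several parts of this stand.

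- **Timing.** A reader might infer that a subject in hospital with DKA must be withdrawn at once and the record closed. The documents do not say so: withdrawal could follow the acute episode, and section 11.3 applies only if the event is unresolved at that point. Severe hypoglycemia as defined in section 11.2 is usually brief, and many episodes will have ended before the site hears of them.
- **Source records.** Sections 11.3 and 11.4 ask for hospital records, including discharge summaries. Sections 9.8 and 16.3.1.1 require the eCRF to agree with source. A site could reasonably correct an AE form from the discharge record of the same event. However, nothing says that record collection continues after exit, and section 11.3 gives sites a reason not to make the entry.
- **Planned analyses.** The glycemic safety measures are incidences, which are complete. Neither document plans a summary of outcome codes, so a higher share coded as unresolved would distort no specified result.
- **CEC.** Section 12.1 has the committee judge the investigator's classification and causality, neither of which is defined by the resolution date. The study-continuation review in section 9.11.2 covers UADEs and device-related DKA or severe hypoglycemia, not every case.
- **Consistency.** The not-recovered code is itself an outcome, so sections 11.1 and 11.3 do not contradict each other.

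What remains is that no text carries a later outcome, a late sequela or a death into the study data for a serious event open at exit.

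**Conclusion.** The point holds as a gap in safety data collection. It is of lower severity and is best treated as a cheap improvement. For an SAE, DKA or severe hypoglycemia event unresolved at withdrawal or at Visit 12, the end date, final outcome and sequelae need not reach the database; where the event itself led to withdrawal, it has set off its own cut-off.

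The size is small: at most about 1.2 expected DKA or severe hypoglycemia events, or about 0.6 in the study period alone. This assumes that the pivotal trial's rate carries over and that exposure is at its maximum. Only the unresolved part of those events is exposed, plus an unknown number of other SAEs near Visit 12. Loss is possible, not certain, because withdrawal timing is undefined and discharge records may show the outcome.

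A reader might go further and infer that the truncated outcomes could amount to all of the serious glycemic safety data. The documents do not support that: occurrence, diagnosis, causality and treatment are still recorded, and severe hyperglycemia is not listed as a reason for withdrawal. The primary analysis, the sample size and the power are unaffected.

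**What to change.** The change concerns data collection only.

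1. In section 9.10, exempt from the no-further-data sentence any SAE, SADE, UADE, DKA, severe hypoglycemia or severe hyperglycemia event that is open at exit.
2. In section 11.3, exempt the same events from the sentence excluding an eCRF entry. State that their outcome is collected by telephone or from medical records until the event is resolved, the subject's condition is stable, or the subject is lost to follow-up, and that the AE eCRF is then updated with end date and final outcome.
3. Send the update to the CEC where it reviewed the event.
4. Match the SAP safety sections to this window.
5. Reconcile sections 9.10 and 9.11.1, the Synopsis and Table 3 on what follows DKA or severe hypoglycemia. Which rule applies is a clinical decision for the sponsor and investigators; the data-collection change is needed either way.

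Non-serious events outside this list can keep the current rule. The cost is a sentence or two in each section, telephone or record follow-up of a few subjects, and possibly a short wait for database lock.
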